#### Phase 1 safety data for selinexor

For the two ongoing clinical trials (KCP-330-001 and KCP-330-002), a total of 97 patients comprise the safety population as of the 31 May 2013 data cut-off (over 130 patients have been dosed to date, but the data sets reported here are through 31 May 2013).

KCP-330-001: A Phase I Study of the Safety, Pharmacokinetics and Pharmacodynamics of Escalating Doses of the Selective Inhibitor of Nuclear Export (SINE) KPT-330 in Patients with Advanced Hematological Malignancies

The AEs for AML patients (Arm 2) in this study are summarized in the table below.

KCP-330-001 (AML cohort, n = 16): Toxicities attributed to selinexor

Adverse Event		Gr	ade		Total
Adverse Event	1	2	3	4	Lotal
Cardiovascular					
Hypotension	1 (6%)		1 (6%)		2 (13%)
Gastroenterological					
Anorexia	2 (13%)	5 (31%)			7 (44%)
Weight loss	5 (31%)				5 (31%)
Diarrhea	1 (6%)	1 (6%)			2 (13%)
Nausea	6 (38%)	2 (13%)	1 (6%)		9 (56%)
Vomiting	5 (31%)				5 (31%)
Heme					
Neutrophil count decreased				1 (6%)	1 (6%)
Platelet count decreased				2 (13%)	2 (13%)
Lab abnormalities					
Aspartate aminotransferase increased	1 (6%)		1 (6%)		2 (13%)
Hypokalemia			1 (6%)		1 (6%)
Hyponatremia	2 (13%)				2 (13%)
Neurology					
Headache			2 (13%)		2 (13%)
Ophthalmology					
Blurred vision	3 (19%)				3 (19%)
Systemic					
Fatigue	1 (6%)	5 (31%)	2 (13%)		8 (50%)

AEs were counted for each patient once as the highest grade AE experienced

Patients entering this study have heavily pretreated hematologic malignancies. The most common AEs, which are also observed in patients with advanced metastatic solid tumors, are gastrointestinal (GI) in nature. These are Grade 1-2 events are generally responsive to standard supportive care measures. Diarrhea is observed in some patients though relationship to study drug is unclear. Dysgeusia is primarily reported as a metallic taste. Thrombocytopenia is seen, but no bleeding events have been observed, and several patients with Grade 4 thrombocytopenia have remained on therapy for months with intermitted glucocorticoids and/or infrequent transfusions, and good disease control. Severe neutropenia has been relatively uncommon and there is only one case of possibly related febrile neutropenia to date.

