#### COMMON, SOME MAY BE SERIOUS

In 100 people receiving selinexor, more than 20 and up to 100 may have:

- Nausea and/or vomiting
- Fatigue or loss of energy
- Loss of appetite
- Diarrhea

- Weight loss
- Low platelets
- Decrease in red blood cells
- Low sodium

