#### OCCASIONAL, SOME MAY BE SERIOUS

In 100 people receiving selinexor, from 4 to 20 may have:

- Change in taste
- Dehydration
- Dizziness
- Constipation
- Confusion
- Shortness of breath
- Visual changes including blurred vision
- Low neutrophil count
- Low white blood cell count
- Increased creatinine
- Dry mouth
- Sepsis

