#### Analysis of secondary endpoints

- 1. Response duration will be caluated among patients who achieve a response of HI, mCR, PR or CR using Kaplan-Meier methodology. Median duration of response and the corresponding 95% confidence interval will be estimated.
- 2. The frequency of stable disease will be tabulated and exact 95% confidence intervals will be estimated.
- 3. The response rate and response duration will also be described for the generally poor-risk therapy-related MDS patients enrolled on this study (therapy-related MDS accruals may approach ~ 50%, as seen in MSKCC protocol 06-054). The response rate will be estimated along with an exact 95% confidence interval to evaluate the proportion of patients who have

- CR, PR, mCR or Hl. Median response duration and corresponding 95% confidence intervals will be estimated.
- Overall survival from the time of study enrollment will be caluated using Kaplan-Meier methodology. Overall survival curves will be displayed for the study population along with selected quantiles and corresponding 95% confidence intervals of survival.
- 5. Since Selinexor may require chronic dosing to maintain its effect, the overall tolerability and safety of chronic Selinexor dosing will be described on patients throughout all cycles of treatment who have received at least 1 dose of selinexor. Tolerability will be assessed by calculating the proportion of patients who withdraw consent due to chronic low-grade (1/2) toxicity. Safety will be calculated by determining the proportion of patients who have any toxicity listed in section 11.0. This will be calculated overall at each treatment cycle and separately by the Selinexor dose received at the time of the selected toxicity. Proportions and exact 95% confidence intervals will be calculated.
- Descriptive statistics will be used to explore the relationship between the results of the
  pharmacodynamics studies and therapeutic response or study entry disease parameters.
  The Wilcoxon rank-sum statistic or Fisher's exact test may be used to assess these
  associations.

Accrual rates and study duration

It is expected that the study will accrue 1-2 patients per month, resulting in completion of accrual in 10-20 months.

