#### Total WBC Count

The total WBC count is typically decreased due to the disease process. However, further reductions in the WBC count are not clinically relevant. Reductions in other WBC subsets may be clinically meaningful and will continued to be entered per MSK guidelines.

MSKCC will cross-reference Karyopharm's IND and will be responsible for all safety monitoring. All SAEs will be reported to the MSKCC IRB. The safety of the study will be monitored by the MSKCC Data and Safety Monitoring Committee.

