Alternatives: For patients considering this trial as second-line therapy, standard second-line treatments would include supportive care or another study drug in an alternate clinical trial, since for patients considering this trial, there are no standard treatment options.

Confidentiality: Every effort will be made to maintain patient confidentiality. Research and hospital records are confidential. Patients' names and any other identifying information will not be used in reports or publications resulting from this study. Other authorized agencies and appropriate internal personnel (e.g. qualified monitors from MSKCC) and external personnel (Karyopharm, the manufacturer of selinexor), its authorized agents, the FDA, and/or other governmental agencies) may review patient records as required.

Patient safety: Patients are monitored by physicians and oncology nurses who are very familiar with clinical trials. In the case of an adverse reaction, immediate medical attention is available. In the evenings and weekends, we have a 24-hour urgent care facility for outpatients. The PI or co-PI will also be available at all times to organize any necessary intervention.

Monitoring of data to ensure safety: This study is to be monitored by the institutional IRB. This incorporates an independent data and safety monitoring board established by arrangement with the National Cancer Institute. The analysis of safety will include all patients. Adverse events, including all toxic effects of treatment, will be tabulated individually, and summarized by severity and causality.

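### The Section 14 safety proportion is tied to the Section 11 side-effect list with no grade or attribution condition, so it leaves out severe events the protocol attributes to selinexor while counting any mild listed event

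*Combined protocol and SAP*

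**What the plan says.** Item 5 of the secondary analyses in Section 14.1 describes safety in patients "throughout all cycles of treatment who have received at least 1 dose of selinexor". It first measures tolerability, as the proportion who withdraw consent because of chronic grade 1 or 2 toxicity. It then turns to safety: "Safety will be calculated by determining the proportion of patients who have any toxicity listed in section 11.0". This is to be computed at each cycle and by the dose being taken when the toxicity occurred. "Proportions and exact 95% confidence intervals will be calculated". Item 5 names no minimum grade, no relatedness condition and no baseline rule.

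Section 11 lists side effects in three frequency bands. The list includes blood-count terms such as "Decrease in red blood cells" and "Low white blood cell count". The Adverse Events Reporting text, also in Section 11, counts a pre-existing condition only if it has become worse or more frequent since study drug. It counts an abnormal laboratory value only if the value leads to action or is a clinically significant change from baseline.

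Two other places bear on the point. Section 17.1 promises: "Adverse events, including all toxic effects of treatment, will be tabulated individually, and summarized by severity and causality". Section 16.1 says of total white cells, for data-entry purposes: "However, further reductions in the WBC count are not clinically relevant".

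**The concern.** A list of known side effects is being used as the definition of a safety endpoint. Anything not on the list cannot enter the proportion, whatever its grade or cause. Anything on it enters at any grade, so one episode of grade 1 nausea counts the same as sepsis.

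That matters more here than in a well-studied population. The dosing rationale that precedes Section 3.5 calls this the first selinexor study in MDS and reports poor tolerance in the first two patients. A reader of the trial report would take the by-cycle and by-dose proportions as the main quantified safety result, yet the most severe drug-attributed events could be absent from them.

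**Working it through.** **Plan figures.** Item 5 states no expected safety proportion, so there is nothing to reproduce. The patient number comes from the Simon design. An exact calculation of that design (stop at 0 of 13, success at 3 or more of 20, 5% against 25%) gives type I error 0.074 and power 0.903. The stated maximum of 20 therefore stands, and it has no bearing on this point.

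**Step 1: the phase 1 tables against the Section 11 list.** Source: the KCP-330-001 AML table (n = 16) under Phase 1 safety data for selinexor, events attributed to selinexor.

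| Grade 3 term | Entries | On the Section 11 list? |
|---|---|---|
| Headache | 2 | No |
| Hypotension | 1 | No |
| AST increased | 1 | No |
| Hypokalemia | 1 | No |
| Fatigue | 2 | Yes |
| Nausea | 1 | Yes |

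Off the list: 2 + 1 + 1 + 1 = 5. Total: 5 + 2 + 1 = 8. So 5 of the 8 grade 3 entries are of unlisted types. The table counts each patient once per term and does not show overlap between terms, so the 5 entries represent between 2 and 5 patients.

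The solid-tumor table (KCP-330-002; 1 patient = 2% implies n = 50) adds one grade 3 hypotension and one grade 3 ALT increase, neither of them on the list.

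**Step 2: chance that such events occur here.** Assume the phase 1 rates carry over. P(at least one in 20) = 1 − (1 − p)^20.

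- Grade 3 headache, p = 2/16: 1 − 0.875^20 = 93%.
- Grade 3 hypotension, AST increase or hypokalemia, each p = 1/16: 1 − 0.9375^20 = 72% each.
- At the solid-tumor rate, p = 1/50: 1 − 0.98^20 = 33%.

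The rates are imprecise: exact 95% intervals are 1.6% to 38.3% for 2/16 and 0.2% to 30.2% for 1/16. These figures show that such events are plausible in 20 patients. They do not forecast how many there will be.

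**Step 3: the listed composite, if item 5 means one proportion for any listed event.** The share with at least one event cannot be below the most common single event. With nausea, fatigue and anorexia taken as independent, it is 1 − (1 − p1)(1 − p2)(1 − p3).

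- AML rates (9/16, 8/16, 7/16): floor 56%; 1 − (7/16)(8/16)(9/16) = 1 − 0.123 = 88%.
- Solid-tumor rates (78%, 70%, 68%): floor 78%; 1 − 0.22 × 0.30 × 0.32 = 1 − 0.021 = 98%.

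These three symptoms probably occur together. With positive association the three-event figure lies between floor and independence value: 56% to 88% at AML rates and 78% to 98% at solid-tumor rates. Other listed events can only raise it. With 20 patients, 19/20 gives an exact interval of 75.1% to 99.9%, and 20/20 gives 83.2% to 100%.

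**Step 4: what the composite hides.** A patient with grade 3 headache and grade 1 nausea would count, but because of the nausea. The proportion cannot tell that patient from one with grade 1 nausea alone.

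**The case against.** Much of the rest of the protocol works against a harsher reading. Four stronger conclusions are tempting, and the documents do not support them.

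- **That the trial would miss new harms.** A reader might infer this from the closed list. Section 17.1 tabulates every adverse event by severity and causality. The synopsis calls for CTCAE grading and a causality assessment for all adverse events, and Section 16.1 captures grade and attribution. A grade 3 headache would be recorded and reported. What it would lack is a proportion by cycle and dose with an interval.
- **That the proportion counts the disease.** A reader might infer this from the cytopenia terms. The adverse event definition in Section 11 should keep unchanged baseline cytopenias out, and eligibility does not require a cytopenia at entry. What remains is that item 5 does not refer to that definition.
- **That the proportion cannot show a difference by cycle or dose.** The phase 1 rates are cumulative and come largely from other doses and schedules. The documents give no per-cycle rates, so a per-cycle ceiling is not shown. Item 5 also mentions the selected toxicity, which can be read as a term-by-term calculation. On that reading the composite problem disappears, though the omission of unlisted terms does not.
- **That low white cell count cannot be counted.** Section 16.1 holds all routine blood results in the database, so the item can be derived. The conflict is between the list and the data-entry rule.

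It is also fair to say that the stated objective is tolerability, which item 5 measures separately, and that no test or decision depends on the safety proportion.

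**Conclusion.** The point holds for the item 5 safety proportion. As written, it excludes types of grade 3 event that the protocol attributes to selinexor, 5 of the 8 grade 3 entries in the AML table, and any toxicity new to MDS. It also counts listed events of any grade. The omission follows from comparing the list with the tables and needs no assumption.

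The claim that the figure says little about severe harm rests on reading item 5 as one composite and on phase 1 rates carrying over: a cumulative floor of 56% (AML) or 78% (solid tumor), and about 88% or 98% for three events under independence. Two smaller inconsistencies remain: item 5 does not cite the adverse event definition in Section 11, and low white cell count is listed although Section 16.1 treats further falls as not relevant for data entry.

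This is a descriptive secondary analysis. It should be corrected, but it does not affect the primary endpoint or the design.

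**What to change.** In Section 14.1 item 5, replace the reference to toxicities listed in Section 11.0 with adverse events of any term that meet the Section 11 definition, that is, new or worsened from baseline. Report, overall and by cycle and dose, with exact 95% intervals:

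- the proportion with any event of grade 3 or higher;
- the proportion with any event of grade 3 or higher that is at least possibly related;
- the proportion for each term.

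Keep the Section 11 list as a named subset under the same definition. Reconcile low white cell count with Section 16.1, either by deriving it from the CBC results already in the database or by dropping it from the listed set.

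The cost is one revised sentence, a reconciling line and a few more descriptive tables. Grade, attribution and blood results are already captured, so no extra patients, visits or data are needed. The intervals will be wide: with 20 patients, 0/20 gives 0% to 16.8% and 1/20 gives 0.1% to 24.9% (the mirror images of 20/20 and 19/20 above), and the cycle and dose subgroups will be less precise where they contain fewer patients.

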#### 15.1 RESEARCH PARTICIPANT REGISTRATION AND RANDOMIZATION PROCEDURES

#### 15.2 Research Participant Registration

Confirm eligibility as defined in the section entitled Criteria for Patient/Subject Eligibility.

Obtain informed consent, by following procedures defined in section entitled Informed Consent Procedures.

During the registration process registering individuals will be required to complete a protocol specific Eligibility Checklist.

All participants must be registered through the Protocol Participant Registration (PPR) Office at Memorial Sloan-Kettering Cancer Center. PPR is available Monday through Friday from 8:30am – 5:30pm at [contact]. Registrations must be submitted via the PPR Electronic Registration System (http://ppr/). The completed signature page of the written consent/RA or verbal script/RA, a completed Eligibility Checklist and other relevant documents must be uploaded via the PPR Electronic Registration System.

#### 15.3 Randomization

This is an open-label phase 2 study. No randomization will be performed.

#### 16.1 DATA MANAGEMENT ISSUES

A research study assistant (RSA) will be assigned to study. The responsibilities of the RSA include project compliance, data collection, extraction and data entry, data reporting, coordination of the activities of the protocol study team and, and of the flow of regulatory paperwork. Study accrual is estimated to to take 1.5 years, and it is estimated that the study will be complete approximately 9 months from the date of the last registration.

The data collected for the study will be entered into a secure database (CRDB). All routine blood test results required per the protocol will be captured in CRDB in addition to baseline medical conditions and disease information, response assessments, off-study documentation, and toxicity grade and attribution. Source documentation will be available to support the computerized patient record.

Lab toxicities will be routinely assessed by the PI. The following labs are considered common toxicities for the disease under study and therefore should be considered not clinically relevant for data entry purposes.

#### Total WBC Count

The total WBC count is typically decreased due to the disease process. However, further reductions in the WBC count are not clinically relevant. Reductions in other WBC subsets may be clinically meaningful and will continued to be entered per MSK guidelines.

MSKCC will cross-reference Karyopharm's IND and will be responsible for all safety monitoring. All SAEs will be reported to the MSKCC IRB. The safety of the study will be monitored by the MSKCC Data and Safety Monitoring Committee.

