- 6. CBC with differential and reticulocyte count: include hemoglobin, hematocrit, mean corpuscular volume, mean corpuscular hemoglobin, mean corpuscular hemoglobin concentration, white blood cell (WBC) count, WBC differential, red blood cell count, reticulocytes, lymphocytes, monocytes, neutrophils, band neutrophils, eosinophils, platelets. WBC differential may be automated or manual. May be performed at MSKCC or local laboratory.
  - CBC with differentials to be performed at screening, cycle 1 day 1, and on days 7, 14, 21 (+/- 1 day ), cycles 2 and beyond on days 1, 14 (+/- 3 days), or more often as clinically indicated, and at the End of Study visit.
- 7. **Chest Radiograph:** both posteroanterior and lateral films should be obtained at baseline. Note: this test does not need to be repeated if results are available from a CT of chest or chest X-ray (PA and laeteral views) performed 30 days prior to C1D1. This test is done to ensure the absence of active pulmonary disease prior to therapy and as a baseline for comparison in the event that patients develop pulmonary adverse effects during the study.
- 8. Selinexor Drug Administration: patients will receive selinexor twice weekly

orally at a starting dose of 60mg per dose. Selinexor will be given for 2 weeks, followed by 1 week of no therapy. The scheduled dosing days should be the same days in each week. One cycle is 21 days or 4 doses (with the following week off).

**9. Blood and bone marrow tests for pharmacodynamics**: blood samples (7ml EDTA, 2ml EDTA, and/or PAXgene)

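### Section 14 counts low white blood cell count as a safety toxicity, but Section 16 takes total WBC falls out of toxicity entry, and the plan does not say which data the count uses

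*Combined protocol and SAP*

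**What the plan says.** Four parts of the protocol bear on this.

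- **Section 14.1, Analysis of secondary endpoints, item 5.** Safety is assessed by "determining the proportion of patients who have any toxicity listed in section 11.0". The result is given by treatment cycle and by the dose being taken when the toxicity occurred, with exact 95% confidence intervals, in patients who took at least one dose. No Section 11 item is exempted.
- **Section 11.1, list of occasional side effects.** The list is introduced by "In 100 people receiving selinexor, from 4 to 20 may have" and includes "Low white blood cell count". Low neutrophil count is a separate entry on the same list.
- **Section 16.1, Data Management Issues, with its Total WBC Count paragraph.** Certain laboratory toxicities common in this disease "should be considered not clinically relevant for data entry purposes". Total WBC is the one named: it is typically low because of the disease, but "further reductions in the WBC count are not clinically relevant". The paragraph then draws a contrast: "Reductions in other WBC subsets may be clinically meaningful and will continued to be entered per MSK guidelines".
- **Section 16.1 again, and Section 10, Study Assessments Footnotes.** "All routine blood test results required per the protocol will be captured in CRDB", and the protocol-required CBC includes "white blood cell (WBC) count, WBC differential, red blood cell count". Toxicity grade and attribution are named as a separate item in the database.

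Section 17.1 (Monitoring of data to ensure safety) adds that each type of adverse event gets its own tabulation, with severity and causality.

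**The concern.** Item 5 asks for a count of a listed event while the entry rule directs staff not to treat that event as relevant. Neither section refers to the other, and Section 14 does not name its data source.

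If the analyst works from entered toxicities, which is natural because Section 17.1 wants severity and causality and a raw CBC value carries no causality, the low white count line would be empty or nearly so. A reader of the report could not tell whether that zero means no leukopenia or no entry. The risk is misreading one line of the safety table in a drug whose own side-effect list includes this event.

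**Working it through.** **Inputs**

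- Denominator: at most 20 treated patients (Section 14.1).
- Assumed frequency of low white count: 4% to 20%, the Section 11.1 band. Applying it to this MDS population is an assumption.
- Earlier figure: KCP-330-002 toxicity table (Section 3.2), 2 patients (4%) with decreased white cells, one grade 2 and one grade 3. The denominator of 50 is inferred from 1 patient being shown as 2%.
- Other toxicities in the same table: nausea 78%, fatigue 70%, anorexia 68%.

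**The plan's own figure.** The 20 comes from the two-stage design: stop if 0 of 13 respond, promising if at least 3 of 20 respond. Exact enumeration gives type I error 0.0736 at a 5% response rate and power 0.903 at 25%. Both meet the 0.10 limits, and a search returns this as the minimax design. The design is used here only as the source of the denominator.

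**If no low white counts are entered.** The reported result is 0/20. The exact 95% upper limit is 1 − 0.025^(1/20) = 16.8%. This would hold at any true rate.

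**If they are all recorded.** The expected count is 20p, and the chance of a genuine zero is (1 − p)^20.

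| True rate p | Expected cases | Chance of a genuine 0/20 | Chance of at least one |
|---|---|---|---|
| 4% | 0.8 | 0.96^20 = 44.2% | 55.8% |
| 10% | 2.0 | 0.90^20 = 12.2% | 87.8% |
| 20% | 4.0 | 0.80^20 = 1.2% | 98.8% |

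For comparison, the exact 95% intervals would be 0.1% to 24.9% for 1/20 and 5.7% to 43.7% for 4/20.

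**Effect on the pooled proportion with any Section 11 toxicity.** Suppose the other toxicities affect a proportion q and low white count occurs independently at rate w. Dropping low white count then lowers the pooled figure by (1 − q)w.

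- q = 78% (nausea alone): 0.22 × 0.04 = 0.9 points, up to 0.22 × 0.20 = 4.4 points.
- q = 20% (an outer bound, with a single other toxicity at that rate): 0.80 × 0.04 = 3.2 points, up to 0.80 × 0.20 = 16 points.

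The first case is much closer to the earlier data, and even it counts only nausea. Once fatigue, anorexia and the rest are included, the loss is smaller still. By-cycle and by-dose proportions can be affected in the same way, but the documents give no per-cycle rates from which to size that.

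**The case against.** A reader might infer that the low white count rate will be 0% by construction, or that the database discards the information. The documents do not support either.

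- The WBC values are kept. Section 16.1 puts all required routine blood results in the database, and only toxicity entry is limited. Section 14 names neither toxicity forms nor laboratory values as its source, so derivation from laboratory values remains open.
- Section 11.1 (Adverse Events Reporting) makes a laboratory abnormality an adverse event if it leads to discontinuation, delay, dose modification or intervention, or if the investigator judges it clinically significant. Section 16.1 largely settles the judgement route in advance, but it does not expressly override the others. An event with consequences could still be recorded.
- The closest related signal is retained, because neutrophils and other subsets are still entered. A patient missed altogether would need a fall in total WBC with no recorded neutropenia and no other listed toxicity.
- Item 5 can be read as one pooled proportion, and that would barely move.
- At the 4% seen in the earlier solid-tumour study, a true 0/20 is unremarkable. An interval reaching 16.8% does not rule out most of the Section 11 band.

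All of this stands and limits the size of the point. It does not remove the conflict. Item 5 refers to the dose at the time of a selected toxicity and Section 17.1 tabulates events one by one, so an individual low white count line is a fair expectation. Capture only through events that changed treatment would be selective.

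**Conclusion.** The point holds as a minor inconsistency between Sections 11, 14 and 16. If item 5 is built from entered toxicities, low white count would be reported at or near 0/20 (95% interval 0 to 16.8%) whatever its true rate, against 0.8 to 4 expected cases at 4 to 20%. This rests on two assumptions: that entered toxicities are the source, which the plan leaves unstated, and that the Section 11 band applies to these patients.

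The effect is on the individual low white count line, and slightly on the by-cycle and by-dose figures. A reader might go further and conclude that neutropenia reporting or the overall safety proportion is compromised. Neither follows, because subsets are still entered and the pooled figure is dominated by common toxicities. The primary endpoint, sample size and error rates are unaffected.

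**What to change.** Reconcile the sections with one sentence in Section 14 or Section 16, choosing one of two routes:

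1. **Derive it.** For item 5, take low white count from the CBC values already in the database, graded by CTCAE 4.03, counted only when worse than the baseline grade, and reported as a laboratory shift without attribution. This is preferable because the data exist.
2. **Exclude it.** Take total WBC out of item 5 and footnote that it was not collected as a toxicity, so that a zero is not read as absence of leukopenia.

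The first route costs a short extra derivation and no new data entry. Its drawback is that it will count some shifts that do not meet the adverse event definition in Section 11.1, which is why they need the laboratory label. The second costs only the footnote but gives up the information.
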